12.3 Vital Signs

Descriptive statistics will be presented by visit for the actual values and the changes from baseline for each vital sign. The difference between treatment groups (pooled SB623 - sham surgery) in the mean change from baseline will also be presented. For each vital sign, the one-sample t-test will be used to test whether the mean change from baseline equals 0 for each post-baseline time point. The two-sample t-test will be used to test whether the mean changes from baseline are equal for the two treatments (pooled SB623 vs. sham surgery). Abnormal vital sign values will be flagged in the data listings. The values in Table 4 are considered vital sign abnormalities.

Table 4. Abnormal Vital Sign Values

| Parameter | Abnormal Value |
|--------------------------|-----------------------|
| Fever | > 38.4°C |
| Tachycardia | >115 beats/minute |
| Bradycardia | < 50 beats/minute |
| Systolic Blood Pressure | > 150 mmHg |
| Diastolic Blood Pressure | > 95 mmHg |
| Hypotension (systolic) | < 85 mmHg |
| Respiratory Rate | > 20 breaths/minute |

12.4 Other Analyses

Medications will be coded using the World Health Organization Drug Dictionary. The number and percentage of subjects taking each type of concomitant medication will be summarized based on the World Health Organization Anatomical Therapeutic Chemical (WHO ATC) Level 4 Class code and generic name.

The number and percentage of subjects with any antibodies to donor HLA antigens and the number and percentage of subjects with an increase in antibody level from baseline will be presented by visit.

1.0 INTRODUCTION

The purpose of this addendum to the Statistical Analysis Plan for the TBI-01 main study is to (1) provide the justification for imputation of the baseline FMMS score for one patient and (2) to document that the CSR will include additional reporting due to post-hoc analyses.

2.0 JUSTIFICATION FOR IMPUTATION OF THE BASELINE FMMS SCORE FOR ONE PATIENT

For one subject in the mITT population, the baseline FMMS evaluation was performed on the incorrect side. The baseline FMMS score is required in order to calculate change from baseline in the FMMS score at Week 24, the primary study endpoint. There is no data handling convention specified for this situation in the Statistical Analysis Plan. As a post-hoc solution, the baseline value for this subject was imputed as defined below.

The initial step in the imputation was to identify baseline variables that measure the severity of TBI. The variables selected were the Motricity Index (MI) scores (upper and lower) and the baseline Glasgow Outcome Scale - Extended (GOS-E) score. The MI is used to measure strength in the upper and lower extremities after stroke, with the upper and lower scores evaluated on the affected side. The GOS-E score measures the level of disability. For subjects in the mITT population with non-missing baseline FMMS scores, the relationship between these variables and the baseline FMMS score was estimated by performing a linear regression (SAS PROC GLM), with the baseline FMMS score as the dependent variable and the MI and GOS-E scores as independent variables. The parameter estimates obtained from the linear regression were then applied to the subject missing a baseline FMMS evaluation in order to impute a baseline FMMS value. This imputed value was used in the analysis.

A sensitivity analysis on this result was then performed by removing the imputed baseline FMMS value from the primary endpoint analysis. By removing this imputed value, this subject was excluded from the sensitivity analysis.

Since the baseline FMMS evaluation on the correct side was missing, the choice was either to impute the missing value or to exclude the subject from this analysis. As the intent of analyses based on the mITT population is to include all randomized subjects who completed the surgical procedure, the primary analysis was based on imputing this value, but, as described above, a sensitivity analysis was performed with this subject excluded.

3.0 EXPANDED STUDY REPORTING FOR POST-HOC ANALYSES

Some post-hoc analyses were added after unblinding of the results of the interim analysis. The tables and figures presenting the results of these post-hoc analyses will be included in the CSR: these analyses will be numbered as 12.x.x.

1.0 INTRODUCTION

The purpose of this Supplement for Japanese Submission to the main Statistical Analysis Plan (SAP) for the TBI-01 study is to describe the additional analysis and tables to be included in the submission to the Japanese regulatory authorities. That submission will also include all of the analyses, tables, and listings described in the main SAP. These additional analyses will descriptively characterize results for Japanese sites and rest of the world (United States and Ukraine) sites so as to be able to compare the results for the two groups of sites. Listings will be done only for the whole study population as specified in the main SAP. The Japanese submission will include all of the analyses and table from the main SAP, the Head MRI SAP, the Genotyping SAP, the Antibody SAP, and the Actigraphy SAP. Separate analyses for Japanese subjects will not be performed, except as shown herein.

2.0 EFFICACY AND SAFETY ENDPOINTS

For the mITT Population (see Section 4.2), patients with a Motricity Index UE Scale score at Screening of 10-81 will be considered to have an upper extremity deficit, and patients with a LE Scale score at Screening of 10-78 will be considered to have a lower extremity deficit.

2.1 Primary Efficacy Endpoint

The primary efficacy endpoint is the change from baseline in the Fugl-Meyer Motor Scale (FMMS) score at Week 24 among all patients.

2.2 Secondary Efficacy Endpoints

The secondary efficacy endpoints are as follows:

- Change from baseline in Disability Rating Scale (DRS) score at Week 24 among all patients
- Change from baseline in Action Research Arm Test (ARAT) total score at Week 24 among upper extremity deficit patients (the affected side will be analyzed)
- Change from baseline in Gait Velocity at Week 24 among lower extremity deficit patients (the better of the two trials at the visit will be used for analysis)
- Change from baseline at Week 24 in T scores of NeuroQOL sub-domains:
 - Upper Extremity Function (Fine motor ADL) among upper extremity deficit patients
 - Lower Extremity Function (Mobility) among lower extremity deficit patients
- Global Rating of Perceived Change scores at Week 24 (from baseline) among all patients: assessed by the subject (may be completed by caregiver) and by the clinician

3.0 STATISTICAL CONSIDERATIONS

The statistical analysis of the data obtained from this study will be performed using SAS[®] version 9.4 or higher.

The data collected in this study will be documented using summary tables. Continuous variables will be summarized using descriptive statistics, specifically the number of observations, mean, median, standard deviation, minimum and maximum. Categorical variables will be summarized by frequencies and percentages. For the most part results will be presented for the four treatment

groups separately and the three SB623 dose groups pooled. All results will be presented separately for Japanese sites and Rest of the World sites.

4.0 ANALYSIS POPULATIONS

4.1 Modified Intent-to-Treat Population

The Intent-to-Treat (ITT) population will include all randomized patients. All efficacy analyses will be conducted on the modified ITT (mITT) population, which is defined as all randomized patients who complete the surgical procedure. In analyses based on the mITT population, subjects will be analyzed according to their randomized treatment assignment. Analyses based on the mITT population will be considered the primary analyses of efficacy.

4.2 Safety Population

The Safety population will include all study patients who undergo surgery (implant or sham). All safety analyses will utilize this population. In analyses based on the safety population, subjects will be analyzed according to the actual treatment received.

5.0 SUBJECT DISPOSITION

The numbers and percentages (based upon the ITT Population) of patients in the ITT Population, in the mITT Population, in the Safety Population, who completed the study, and who discontinued from the study before completion will be presented. For subjects who discontinued from the study before completion, the primary reason for early termination will be summarized using frequencies and percentages.

6.0 DEMOGRAPHICS

Subject demographics collected at the screening visit will be summarized using descriptive statistics for continuous variables (age at informed consent) and frequencies and percentages for categorical variables (sex, race, and ethnicity).

7.0 EFFICACY ANALYSES

7.1 Primary Efficacy Endpoint

The primary analysis will be a comparison of the least-squares mean (LSM) change from baseline in the Fugl-Meyer Motor Scale score of SB623 treated subjects (pooling all SB623 doses) to sham surgery control subjects at Week 24. A mixed model repeated measures (MMRM) analysis will be performed with terms for treatment (SB623 or sham surgery), visit, the treatment-by-visit interaction, the baseline Fugl-Meyer Motor Scale score, the baseline Fugl-Meyer Motor Scale score-by-visit interaction, the GOS-E score at screening, and the GOS-E score at screening-by-visit interaction. The Restricted Maximum Likelihood Estimation (REML) procedure will be employed using an unstructured covariance matrix. The LSM and standard error will be presented for the two treatments, together with a 95% confidence interval for the LSM. The difference in LSMs between treatments and corresponding 95% confidence interval will also be presented.

In addition, the primary efficacy endpoint, the change from baseline in the FMMS score at Week 24, will be analyzed to examine dose response. As for the primary analysis, a mixed model repeated

measures (MMRM) analysis will be performed. The model will include terms for visit, the interaction between SB623 dose and an indicator variable for the Week 4 visit, the interaction between SB623 dose and an indicator variable for the Week 12 visit, the interaction between SB623 dose and an indicator variable for the Week 24 visit, the baseline Fugl-Meyer Motor Scale score, the baseline Fugl-Meyer Motor Scale score-by-visit interaction, the GOS-E score at screening, and the GOS-E score at screening-by-visit interaction. The Restricted Maximum Likelihood Estimation (REML) procedure will be employed using an unstructured covariance matrix. Dose will be treated as a continuous variable, and the control treatment will not be included in this analysis. The p-value from the test of the null hypothesis that the coefficient for the interaction between SB623 dose and the indicator variable for the Week 24 visit equals zero will be presented.

For FMMS score, the following imputation rules will be followed for missing data:

- a) impute missing individual items at post-baseline visits using the Last-Observation-Carried-forward (LOCF) method.
- b) impute missing individual items at baseline in the following two ways (i. imputed with a score of 0; ii. imputed with the first observed post-baseline value).

7.2 Secondary Efficacy Endpoints

The change from baseline in the Disability Rating Scale (DRS) score at Week 24 among all patients, the change from baseline in the Action Research Arm Test (ARAT) total score at Week 24 among upper extremity deficit patients, the change from baseline in Gait Velocity at Week 24 among lower extremity deficit patients, and the change from baseline at Week 24 in the two NeuroQOL subdomain T scores (Upper Extremity Function (Fine Motor ADL) and Lower Extremity Function (Mobility)) among upper extremity deficit patients and lower extremity deficit patients, respectively, will each be analyzed in a manner analogous to that for the primary efficacy endpoint.

The proportions of SB623 treated subjects (pooling all SB623 doses) scoring either 7 (much better) or 6 (a little better, meaningful) on the Global Rating of Perceived Change (from Baseline) - Subject at Week 24 and on the Global Rating of Perceived Change (from Baseline) - Clinician at Week 24 will be compared to the corresponding proportions of sham surgery control subjects using a logistic regression model with a term for treatment (SB623 or sham surgery) and the baseline Fugl-Meyer Motor Scale score and the GOS-E score at screening as continuous covariates. The endpoints for these analyses are dichotomized variables based on the Global Rating of Perceived Change score (≥ 6 vs. < 6).

8.0 SAFETY ANALYSES

The safety analyses will be performed on the safety population.

The summary of AEs will be limited to treatment emergent AEs, which are defined as any adverse event with onset on or after the initiation of treatment or any adverse event already present that worsens in intensity following exposure to study treatment.

The number and percentage of subjects with at least one adverse event, at least one serious adverse event (SAE), and at least one adverse event that led to discontinuation from the study will be presented. The number and percentage of subjects having an adverse event in each System Organ Class (SOC) and having each individual type of adverse event (Preferred Term) will be presented. This analysis will also be performed for serious adverse events (SAEs). Adverse events will also be summarized at the event level by SOC/Preferred Term and relationship to study product.

1.0 INTRODUCTION

This document details the analysis plan for the analyses involving genotyping variables for the study entitled “A Double-Blind, Controlled Phase 2 Study of the Safety and Efficacy of Modified Stem Cells (SB623) in Patients with Chronic Motor Deficit from Traumatic Brain Injury (TBI)”. It describes the proposed efficacy and safety analyses, including planned summary tables, by-subject data listings, and figures. This document is a supplement to the main statistical analysis plan (SAP).

2.0 OBJECTIVES

The overall objective of the study is to evaluate the safety and efficacy of SB623 cells stereotactically implanted in the brains of patients with TBI.

The objectives of the genotyping statistical analyses are to evaluate the efficacy of intracranial administration of SB623 cells with respect to genotyping variables and to evaluate the effect of intracranial administration of SB623 cells on the primary efficacy endpoint, the change from baseline in the Fugl-Meyer Motor Scale score at Week 24, stratified by the values for various genotyping variables.

3.0 STUDY DESIGN

3.1 Overview

This is a double-blind, sham surgery controlled study of stereotactic, intracranial injection of SB623 cells in patients with fixed motor deficits from TBI. The study will be conducted at approximately 30 sites in North America (i.e., United States), Eastern Europe (i.e., Russia and Ukraine), and Asia Pacific (i.e., Japan).

Table 1 in the main SAP lists the procedures to be followed throughout the course of the study. Blood for genotyping will be collected at Baseline.

3.2 Method of Assigning Subjects to Treatment

Two groups, Group 1 and Group 2, will receive SB623 and sham surgery, respectively, in a 3:1 randomization scheme. Group 1 will be further randomized in a 1:1:1 ratio to receive either 2.5 million, 5 million, or 10 million SB623 cells. Randomization will be performed via an interactive web/voice response system (IXRS). For subjects enrolled outside of Japan, the randomization will be stratified by Glasgow Outcome Scale-Extended (GOS-E) score (i.e., scores 3, 4, 5 or 6); for subjects in Japan, the randomization will not be stratified.

3.3 Blinding

This is a double-blind study. The blind will be maintained by strict role definition and procedures as described in the protocol.

3.4 Changes to the Protocol-Specified Analyses

No changes were made to the protocol-specified analyses.

4.0 EFFICACY AND SAFETY ENDPOINTS IN THIS STATISTICAL ANALYSIS PLAN

4.1 Primary Efficacy Endpoint

The primary efficacy endpoint in the study is the change from baseline in the Fugl-Meyer Motor Scale (FMMS) score at Week 24 among all patients.

4.2 Safety Endpoints

The safety endpoints of interest in this SAP are the presence of serious adverse events (SAEs) and the number of SAEs per patient.

5.0 STATISTICAL CONSIDERATIONS

5.1 General Methodology

The statistical analysis of the data will be performed using SAS[®] version 9.4 or higher. All statistical tests will be performed at the 0.05 significance level.

Continuous variables will be summarized using descriptive statistics, specifically the number of observations, mean, median, standard deviation, minimum and maximum. Categorical variables will be summarized by frequencies and percentages. For the most part results will be presented for the four treatment groups separately and the three SB623 dose groups pooled. The three SB623 dose groups will be pooled for all statistical tests comparing SB623 to sham surgery, except where noted otherwise (e.g., dose response analyses).

Data listings will be sorted by treatment group and subject ID. All date fields will be presented in a format of ddmmmyyyy (i.e., 01Jan2018) in the listings.

5.2 Adjustments for Covariates

The primary efficacy endpoint, the change from baseline in the Fugl-Meyer Motor Scale (FMMS) score at Week 24, will be analyzed using an analysis of covariance (ANCOVA) model with adjustment for the baseline FMMS score as a continuous covariate.

5.3 Handling of Dropouts and Missing Data

Every effort will be made to minimize the number of dropouts and to document reasons for dropping out.

For FMMS score, the following imputation rules will be followed for missing data:

- (a) Impute missing individual items at post-baseline visits using the Last-Observation-Carried-Forward (LOCF) method.
- (b) Impute missing individual items at baseline in the following two ways (i. imputed with a score of 0; ii. imputed with the first observed post-baseline value).

If there are no missing individual items for FMMS score at baseline, then the FMMS results will be shown only once, rather than once for each case specified in (b) above.

5.4 Multicenter Study

Approximately 52 subjects will be randomized into the study at approximately thirty (30) sites in North America (i.e., United States), Eastern Europe (i.e., Russia and Ukraine), and Asia Pacific (i.e., Japan). A maximum of 12 subjects will be enrolled at each Assessment site, and a maximum of 16 subjects will be enrolled or treated at each Surgery or Comprehensive site, respectively.

5.5 Multiple Comparisons / Multiplicity

Multiplicity considerations will not be taken into consideration in the analyses for this Phase 2 study.

5.6 Examination of Subgroups

The primary analyses of the primary efficacy endpoint will be performed on the following genotype subgroups of interest, which are determined once, at Baseline, with a blood test:

1. HLA typing

2. Presence of BDNF (Brain derived neurotrophic factor) mutation
3. ApoE locus

5.6.1 HLA Genotype

HLA typing compares donor to recipient at each of two alleles for each of the following loci:

- a. HLA-A (0 mismatch, 1 mismatch, or 2 mismatches)
- b. HLA-B (0 mismatch, 1 mismatch, or 2 mismatches)
- c. HLA-C (0 mismatch, 1 mismatch, or 2 mismatches)
- d. HLA-DRB1 (0 mismatch, 1 mismatch, or 2 mismatches)
- e. HLA-DQB1 (0 mismatch, 1 mismatch, or 2 mismatches)

These results generate the following 3 HLA subgroup categories (by adding up the number of mismatches at each locus), which will be used for the subgroup analyses:

- High degree of mismatch (8-10 mismatches)
- Moderate degree of mismatch (4-7 mismatches)
- Low degree of mismatch (0-3 mismatches)

5.6.2 Presence of BDNF Mutation

For this variable, there are four possible genotype groups.

| BDNF Group | Genotype |
|-------------------|-----------------|
| A | Val/Val |
| B | Val/Met |
| C | Met/Met |
| D | Other |

The subgroup analyses will be performed for the following subgroup categories, which have been dichotomized according to whether the subject has at least one Met allele:

| BDNF Subgroup | BDNF Groups |
|-------------------------|--------------------|
| No Met alleles | A, D |
| At least one Met allele | B, C |

5.6.3 ApoE Genotype

For this variable, the groups are as follows:

| Apo Group | ApoE2 | ApoE3 | ApoE4 | Description |
|------------------|--------------|--------------|--------------|--------------------|
| A | 0 | 0 | 2 | Homozygous ApoE4 |
| B | 0 | 1 | 1 | Heterozygous ApoE4 |
| C | 1 | 0 | 1 | Heterozygous ApoE4 |
| D | 0 | 2 | 0 | Homozygous ApoE3 |
| E | 1 | 1 | 0 | Heterozygous ApoE2 |
| F | 2 | 0 | 0 | Homozygous ApoE2 |
| Other | | | | None of the above |

The subgroup analyses will be performed for the following subgroup categories:

| Apo Subgroup | Apo Groups |
|---------------------------|-------------------|
| At least one ApoE4 allele | A, B, C |
| No ApoE4 alleles | D, E, F, Other |

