15.5 HLA typing and ApoE4 and BDNF Val66Met Genotyping

HLA typing (molecular) of each subject will be performed at baseline to allow exploratory analysis of degree of mismatch to SB623 with respect to both efficacy and safety.

Genotyping at the ApoE locus (i.e., to determine if patient is homozygous for ApoE4, E2 or E3, or if patient is heterozygous for E2/E3, E3/E4 or E2/E4) will be performed at baseline.

Assessment of whether BDNFVal66Met mutation is present (yes/no) will be performed at baseline.

A central laboratory will be utilized for sample storage and assay.

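### The genotyping plan counts every ApoE and BDNF 'Other' result as a non-carrier, although the listed genotypes already cover all pairs of the named alleles

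*SAP*

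**What the plan says.** Protocol 15.5 plans ApoE genotyping to establish whether a patient is "homozygous for ApoE4, E2 or E3, or if patient is heterozygous for E2/E3, E3/E4 or E2/E4". For BDNF it plans a binary result: "Assessment of whether BDNFVal66Met mutation is present (yes/no) will be performed at baseline".

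SAP Appendix C turns these into subgroups.

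- **BDNF (5.6.2).** "For this variable, there are four possible genotype groups": A is Val/Val, B is Val/Met, C is Met/Met and D is 'Other', with no further definition. The subgroups are said to be "dichotomized according to whether the subject has at least one Met allele", and the non-carrier row reads "No Met alleles | A, D".
- **ApoE (5.6.3).** Groups A to F are given as counts of each of the three alleles. A seventh row, 'Other', has blank allele counts and is described only as "None of the above". The subgroups are "At least one ApoE4 allele | A, B, C" and "No ApoE4 alleles | D, E, F, Other".

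Appendix C uses these subgroups in the treatment-by-subgroup ANCOVA of Week 24 FMMS change and the dose-response models (section 7.0), and in the Fisher tests and logistic models for serious adverse events (section 8.0).

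**The concern.** Both splits are meant to separate patients who have the allele from those who do not. For 'Other', the SAP gives no allele information: the ApoE4 count is blank, whereas groups D, E and F each show zero, and BDNF group D is undefined. The result still goes into the subgroup labelled as lacking the allele, and no reason is given.

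At stake is the labelling of the exploratory genotype results. Among the compiled outputs, Tables 14.2.22.1 to 14.2.22.4 and 14.2.23.1 to 14.2.23.2 use these subgroups. Figures 14.2.14.2 and 14.2.15.2 describe their patients as having no BDNF mutation and no ApoE4 allele, which may be untrue or unknown for a patient in 'Other'. Carriers placed among non-carriers would pull the two groups together. With 52 patients randomised 3:1, sham has about 52 × 1/4 = 13, so a few such patients could matter there.

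**Working it through.** **1. Do the listed groups leave anything for 'Other'?** The number of unordered pairs from *n* alleles, repeats allowed, is *n*(*n* + 1)/2.

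| Locus | Named alleles | Possible pairs | Listed groups | Pairs left over |
|---|---|---|---|---|
| ApoE | 3 | 3 × 4/2 = 6 | A to F, all distinct (6) | 0 |
| BDNF | 2 | 2 × 3/2 = 3 | A to C, all distinct (3) | 0 |

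The six ApoE groups are E4/E4, E3/E4, E2/E4, E3/E3, E2/E3 and E2/E2, the same six as in Protocol 15.5. No pair of named alleles can fall into 'Other'.

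**2. What can 'Other' hold, and is the rule right for it?**

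| Content of 'Other' | True status | SAP assignment |
|---|---|---|
| Unlisted variant with a named allele other than E4 or Met, or two unlisted variants | Non-carrier | Correct |
| Unlisted variant with E4 or Met | Carrier | Wrong |
| Unresolved result, if coded there | Unknown | Unsupported |

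**3. Does another rule cover genotype?** Appendix C 5.3 has imputation rules for FMMS items only. Section 7.0 leaves missing observations unimputed but does not mention genotype. Neither says what happens to an unresolved genotype or overrides the assignment of 'Other'.

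**4. How large could the error be?** The plan gives no figure to reproduce. Let *N* be the number of patients considered, *k* the number in 'Other', *q* the share of those who are truly carriers, and *p* the carrier prevalence among the rest. The share of the analysed non-carrier group who are really carriers is

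*m* = *kq* / [(*N* − *k*)(1 − *p*) + *k*].

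*N* is 52 overall or 13 in sham. The other inputs are assumptions: *p* from 15% to 35%, *k* from 1 to 3, *q* from *p* up to 100%.

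| Case | *N* | *p* | *k* | *q* | *m* |
|---|---|---|---|---|---|
| All patients, low | 52 | 0.15 | 1 | 0.15 | 0.15 / (51 × 0.85 + 1) = 0.3% |
| All patients, high | 52 | 0.35 | 3 | 1 | 3 / (49 × 0.65 + 3) = 8.6% |
| All 'Other' in sham, low | 13 | 0.15 | 1 | 0.15 | 0.15 / (12 × 0.85 + 1) = 1.3% |
| All 'Other' in sham, high | 13 | 0.35 | 3 | 1 | 3 / (10 × 0.65 + 3) = 31.6% |
| No 'Other' result | any | any | 0 | – | 0% |

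If misclassified carriers respond like other carriers, the expected carrier versus non-carrier difference in that group shrinks to (1 − *m*) of its true size. That is 91.4% in the third-to-last sense of spread over all patients (1 − 0.086) and 68.4% in the extreme sham case (1 − 0.316).

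**5. What does the narrower rule lose?** With ApoE as A, B, C against D, E, F and BDNF as B, C against A, all six and all three genotypes stay classified.

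**The case against.** The strongest reply is that 'Other' is a catch-all that will probably be empty. The BDNF table presents it as a genotype group, which suggests a result that was obtained but not listed. A failed assay yields no genotype, and a patient without a subgroup value would simply drop out of an ANCOVA with a subgroup term. Where both alleles are read, carrier status is known, and often it is non-carrier, as the SAP assumes. For BDNF, treating Met not shown as mutation absent is a defensible reading of the protocol's yes/no variable. Genotypes are also summarised by counts and percentages (main SAP 8.0, Table 14.1.7) and listed by patient (Listings 16.2.4.9 and 16.2.4.10). The table shells are not available, so it cannot be said that the 'Other' count is absent.

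Most of this stands. A reader might infer that failed or indeterminate assays are being analysed as known non-carriers; no section sends such results to 'Other', so that is unproven. Nor is every 'Other' patient of unknown status. It would also be wrong to gauge the harm by how far one patient moves a small sham mean, since any patient does that, correctly classified or not.

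What the reply does not remove is the rule itself. It sends every 'Other' result to the non-carriers, including an unlisted variant paired with E4 or Met, which contradicts the SAP's own criterion.

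**Conclusion.** The point holds as a minor defect of definition. The assignment of 'Other' at both loci does not follow from the stated split by allele, and it would mislabel any 'Other' patient who carries the allele or whose status is unknown.

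Its size cannot be fixed from the documents. Under the assumed inputs, the misclassified share of the non-carrier group runs from 0.3% to 8.6% over all patients. It reaches 31.6% only if three 'Other' results all fall in sham and all are carriers. It is zero if no result is 'Other'.

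A reader might go further and conclude that the rule has blurred a genotype effect or touches the trial's main result. The documents support neither. The first needs a true genotype difference and actual carriers within 'Other'. The second fails because the primary MMRM (main SAP 10.1) has no genotype term; the genotype analyses are exploratory (main SAP 4.3, item 13) and carry no multiplicity control (Appendix C 5.5).

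**What to change.** In Appendix C 5.6.2 and 5.6.3:

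- Set the BDNF non-carrier subgroup to group A and the ApoE non-carrier subgroup to groups D, E and F.
- State which laboratory results are coded as 'Other'.
- Classify an 'Other' result by its observed alleles where these establish carrier status. Otherwise treat it as missing for the genotype subgroup analyses.
- Show the number of 'Other' results by arm in Table 14.1.7.

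The wording cost is a few lines. Any patient of unknown carrier status leaves these subgroup analyses. The genotyping SAP is dated 4 October 2018, and the addendum in the September 2019 compilation records that interim results had been unblinded. A change made after that unblinding must be reported as post hoc. If the 'Other' count is zero, stating so is enough, because no result would change.
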